## Expected outcomes

**Primary outcome:** If the null hypothesis is upheld, this suggests that FFR/RFR measurements are valid even in the presence of severe AS.

## Secondary outcomes

- 1. A description of the range of IMR values in a cohort of patients with severe AS will be a novel and important contribution to the field of interventional cardiology. Furthermore, the change in IMR (microvascular function) in response to valve replacement will be an important finding in this study. If there is a significant decrease in IMR then this indicates that microcirculatory function improves 6 months after aortic valve intervention. Since microvascular function predicts outcomes in patients with AS, IMR evaluation at 6 months after TAVI/SAVR might provide an additional method to risk stratify these patients even after correction of the valve pathology.
- 2. If the “corrected” FFR (at baseline; based on baseline IMR) does not correlate with the post-intervention FFR then a correction of FFR using baseline IMR does not improve the accuracy of FFR in patients with severe AS.
- 3. Compared with SPECT, a correlation of FFR and RFR will be an important contribution. Firstly, this will be a validation of RFR as a resting measure of ischemia in AS patients. Secondly, these data will support the data of a previous study with a different resting measure of ischemia (iFR) or the findings may be in conflict with the previous study, which would be important.

4. Using SPECT as a standard of myocardial ischemia, IMR may improve the ischemia prediction of FFR. This would be an extremely important finding, supporting the routine use of IMR in patients with microvascular disease when coronary artery lesions need assessment by FFR. Because AS is an important clinical condition with reversible microvascular dysfunction, this provides an excellent naturally occurring model for the study of microvascular function and CAD. These findings will be useful in other groups of patients who also have microvascular dysfunction (including patients with heart failure, obesity, diabetes, liver disease, chronic kidney disease and heart transplant patients). Being able to factor-in microvascular dysfunction (using simultaneously measured microvascular resistance) at the time of FFR measurement will permit accurate assessment of the severity of CAD in these patients. This study has the potential to revolutionize the assessment of coronary artery lesions, not just in patients with AS, but in all patients with CAD since the validity of CAD assessment by FFR/NHPRs may, indeed, depend on microvascular function.
5. We hypothesize that in AS patients the measurements will be reproducible such as in other patients, however we expect the RFR to be more reproducible than the FFR which we expect to be more reproducible than the IMR.

### 3. STUDY DESIGN & INTERVENTIONS

#### 3.1 Study Design

A single centre, prospective, cohort study.

#### 3.2 Study duration

The anticipated duration of the study will be 3 years.

#### 3.3 Patient population

Patients undergoing routine cardiac catheterization during preparation for TAVI or SAVR, who are found to have coronary artery disease, will be approached to take part. A transthoracic echocardiography (TTE) will take place at baseline and at 6 months. A TTE is part of the routine care and almost without risk. The TTE will assess systolic function, diastolic function, right and left ventricular function, valvular function, fluid status, pulmonary pressures and shear wave analysis to assess the stiffness of the heart. These two extra TTE's will be necessary to standardize the assessment of the valve pathology, to ensure our patients are good candidates and to assess the status post intervention in comparison to before the valve procedure. Cardiac catheterization is routinely performed in these patients and intra-coronary hemodynamic measurements are routinely used during the assessment of coronary artery disease. SPECT is used to confirm the presence of ischemia. Baseline measurements of coronary artery disease and coronary microvascular function (IMR) will be carried out during the baseline cardiac catheterization if intermediate coronary artery lesions (defined as a coronary artery stenosis in the proximal part of a major coronary artery of 50-90% stenosis). During the six-month cardiac catheterization the coronary artery disease is assessed. During this procedure an additional measure of microvascular function (IMR) will be performed. FFR is routine clinical practice, but the additional measurement of IMR will be investigatory.

### 3.4 Informed consent process

Informed consent should be obtained in accordance to the applicable regulations, the declaration of Helsinki and Good Clinical Practice. All potential patients must give their written consent prior to any study specific procedures. If a patient might be eligible for the study (after a first check of the inclusion/exclusion criteria), the investigator or delegated staff should approach the patient to obtain the written informed consent. During this interview the background of the proposed study and the benefits and risks of the study participation should be explained in detail to the patient. It has to be emphasized that a patient's participation in the trial is voluntary and that the patient may refuse to participate or withdraw from the trial, at any time, without penalty or loss of benefits to which the patient is otherwise entitled. The patient must be given ample time to read the whole patient information and to address questions before signing the consent form. The patient information and a copy of the signed consent form will be handed out to the patient. The patient information as well as the patient informed consent will have the approval of the institution's Review Board and/or Ethics Committee (IRB/IEC) prior to their usage.

### 3.5 Inclusion criteria

1. Patient is older than 18 years and is planned for a cardiac catheterization as part of the work up for TAVI or SAVR.
2. Patient has severe aortic valve stenosis as defined by the European Society of Cardiology.
3. The coronary angiogram cardiac catheterization is elective.
4. The patient has an intermediate (50-90%) coronary lesion that requires further evaluation.
5. The subject is male, or if female, has no childbearing potential or is not pregnant.

### 3.6 Exclusion criteria

1. The procedure is an emergency and/or the patient is unstable.
2. Pregnancy or lactation
3. Haemodynamically unstable patients

4. Killip class III-IV
5. Previous CABG
6. Contra-indications for adenosine administration: severe asthma or pre-existing type 2 AV-block
7. No significant coronary artery disease (<50% stenosis on angiography).
8. Critical coronary artery disease deemed by the Heart Team to require revascularization.
9. Patients will be excluded from the SPECT study (secondary objective) if they have a left main coronary stenosis >50%, severe triple vessel disease, previous myocardial infarction in the same coronary artery & tandem lesions (separated by >10mm) requiring independent evaluation in the same coronary artery since these factors interfere with the SPECT analysis.

### 3.7 Screening and enrolment process

Only if all inclusion criteria are met/exclusion criteria are not met, can the patient be included in the study.

### 3.8 Methodology

Figure 1 summarizes the study flow. Patients admitted electively for a valve work-up and patients admitted through the Emergency department that have to undergo a valve work-up will be approached to take part in the study. All these patients undergo routine cardiac catheterization during preparation for TAVI or SAVR. If they are found to have intermediate coronary artery disease on the angiography, measurements to assess the severity of the lesions and microvascular function (further explained beneath) will be performed during the catheterisation. . Cardiac catheterization is routinely performed in these patients and intra-coronary hemodynamic measurements are routinely used during the assessment of coronary artery disease. SPECT is also used to confirm the presence of ischemia. Baseline intra-coronary measurements of coronary artery disease and coronary microvascular function (IMR) will be carried out in duplicate during the baseline cardiac catheterization if intermediate coronary artery lesions (defined as a coronary artery stenosis in the proximal part of a major coronary artery of 50-90% stenosis by quantitative coronary analysis).

During routine cardiac catheterization, patients with intermediate coronary artery lesions, will undergo hemodynamic assessment of the coronary stenosis according to current ESC guidelines. This entails the use of a pressure wire (Pressure Wire X, Abbott Medical) in the coronary artery distal to the stenosis in order to determine the pressure gradient over the stenosis. Prior to induction of hyperemia, Resting Full cycle Ratio (RFR) is measured before determining fractional flow reserve (FFR). In order to measure a FFR, adenosine at 140 $\mu$ g/kg/min is administered via a peripheral venous infusion catheter. This is routine clinical practice. To address for factors that might cause small changes in these measurements, all measurements will be done twice, without an extra risk to the patient. Two measurements are frequently performed in clinical practice to get a robust measurement. This will also allow us to test the reproducibility of our measurements.

At this time three boluses of room-temperature saline are administered in order to measure the intra-coronary flow during hyperemia by the method of thermodilution. This extra step, which is investigational, adds no additional risk or cost to the patient. However, it permits the calculation of flow and microvascular resistance or IMR (index of microvascular resistance) using Coroflow® software (Coroventis, Uppsala, Sweden). IMR is already clinically indicated in several other groups of patients (with suspected microvascular dysfunction) and is used on a routine basis in patients in our cardiac catheterization laboratory.

In order to assist the Heart Team in deliberation over the ischemic importance of intermediate coronary lesions, SPECT imaging is clinically indicated during the pre-operative/interventional work up. This will be carried out in the Department of Nuclear Medicine according to routine clinical practice under the guidance of [name]. If adenosine cannot be used then regadenoson will be used.

Intra-coronary assessment of intermediate lesions is part of routine clinical practice. The decision to revascularize and the method of revascularization (percutaneous coronary intervention versus coronary artery bypass grafting) of patients with aortic stenosis based on intra-coronary measurements and non-invasive measures of ischemia (SPECT) is discussed by the Heart Team (including the cardiologist and cardiothoracic surgeon) and forms part of routine clinical practice. In patients who do not undergo immediate revascularization, the residual CAD should be reassessed after SAVR/TAVI. Current controversy about the validity of both intra-coronary and non-invasive tests in patients with AS necessitates further evaluation (after valve intervention) since coronary lesions should not be unnecessarily treated (Class III recommendation in the ESC guidelines).

In the patients who will undergo TAVI measurements of LVEDP will be carried out during the TAVI procedure immediately before and after valve implantation. As the catheters are already present in the ventricle of the patient at this point this does not require an extra intervention

of risk (the pressure measured by the catheter will simply be recorded for the study data). Immediately following TAVI, intracoronary hemodynamic assessment of the intermediate study lesions will be performed with measurement of FFR, RFR and IMR. For this assessment the same arterial access used during TAVI will be used. Finally, during the six-month cardiac catheterization the coronary artery disease is assessed. During this procedure additional measurements of microvascular function (IMR) will be performed. Again, FFR is routine clinical practice, given the ambiguity of earlier measurements in the presence of aortic valve stenosis, but the additional measurements of IMR will be investigatory. As discussed before the measurements will be performed in duplicate.

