## PROTOCOL SUMMARY

Aortic stenosis (AS) is the most common primary valve disease leading to surgery or catheter intervention in Europe, with a growing prevalence due to the aging population. Severe AS is associated with significant morbidity and mortality and is treated by surgical valve replacement (SAVR) or transcatheter aortic valve implantation (TAVI). However, significant coronary artery disease (CAD) is reported in more than 60% of patients with AS, and this concomitant CAD needs to be correctly assessed because untreated significant CAD is associated with adverse outcomes. Current guidelines recommend intra-coronary pressure measurement using either fractional flow reserve (FFR) or non-hyperemic pressure ratios (NHPR) for the assessment of intermediate coronary artery lesions before revascularization. However, correctly identifying hemodynamically significant coronary stenoses by FFR or NHPR is difficult in patients with AS because of the hypertrophic remodeling related to the valve pathology, which interferes with coronary blood flow in the microcirculation and reduces the accuracy of FFR and NHPR. This has resulted in substantial controversy in this field of coronary artery disease and there is currently no clear guideline for the management of AS patients with concomitant CAD. Recent technological advances now permit the concomitant evaluation of FFR/NHPR and microcirculatory function at the time of cardiac catheterization. Using this technology, we will simultaneously evaluate the hemodynamic significance of coronary stenoses (using FFR and a NHPR - Resting Full cycle Ratio [RFR]) and the microcirculatory function (Index of Microcirculatory Resistance, IMR) in patients with AS and CAD prior to SAVR/TAVI. One hundred patients with AS and intermediate CAD will be included in the study. Of them Eighty will undergo AVR and at least 58 will undergo the follow-up at 6 Months. During routine pre-valve replacement cardiac catheterization, measurement of intermediate CAD lesions (by FFR and RFR) and IMR will be performed in duplicate using new software. These measures of CAD severity will be compared with a gold standard non-invasive test (single photon emission computed tomography [SPECT]). This will validate the use of RFR and determine if IMR can be used to improve the ischemia prediction of FFR. In addition, the patients undergoing TAVI the LVEDP will be measured immediately before and after valve implantation and FFR, RFR and IMR will be measured after valve implantation. Subsequently, when these patients undergo a post-intervention (whether SAVR or TAVI) evaluation 6 months after valve replacement, the effect of valve replacement on FFR, RFR and IMR (again in duplicate) will be determined. This will be the first study measuring these parameters before and 6 months after valve replacement. The data will be used to calculate a 'corrected' FFR (or RFR) based on microcirculatory function in these patients, which can then be used in the future to correctly evaluate CAD pre-intervention in patients with AS. This will translate into more efficient management of patients with AS. Fewer of these patients will unnecessarily undergo coronary artery bypass grafting or stenting when the CAD does not need to be treated and, conversely, in those who do require treatment of the CAD, revascularization can be carried out during a single surgery/intervention, avoiding multiple high risk procedures in patients who are already at high peri-operative/peri-interventional risk.

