### Secondary outcomes

2. Measurement of IMR in patients with AS prior to intervention and 6 months after SAVR/TAVI.
  - a. Description of the range of IMR values in a cohort of patients with severe AS.
    - i. Do all patients with severe AS have high microvascular resistance as assessed by IMR?
    - ii. Does IMR change significantly 6 months after TAVI/SAVR? If there is a significant decrease in IMR then this indicates that microcirculatory function improves 6 months after aortic valve intervention.
3. Null hypothesis: the “corrected” FFR (at baseline; based on baseline IMR) does not correlate with the post-intervention FFR.
  - a. If the null hypothesis is upheld then a correction of FFR using baseline IMR does not improve the validity of FFR in patients with severe AS.
4. Null hypothesis: using IMR at baseline does not improve the ischemia prediction of FFR. Ischemia is measured by SPECT (Figure 2).
  - a. If the null hypothesis is upheld then IMR does not improve stratification of coronary ischemia based on FFR.

- b. If a significant proportion of patients with SPECT ischemia have a raised IMR this would support the hypothesis that IMR can be used to correct falsely high (negative) FFR measurements.
- 5. Comparison of the diagnostic performance of FFR and RFR with SPECT ischemia (and compare with findings of Yamanaka *et al*).
- 6. Reproducibility of the FFR, RFR and IMR

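### The plan does not mask the SPECT read, the reference standard for secondary objectives 4 and 5, to FFR, RFR and IMR, and does not say whether it precedes catheterisation

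*Combined protocol and SAP*

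**What the plan says.** The Protocol Summary makes SPECT the reference: "These measures of CAD severity will be compared with a gold standard non-invasive test". Two secondary outcomes depend on it. Outcome 4 reads "Null hypothesis: using IMR at baseline does not improve the ischemia prediction of FFR", with ischaemia measured by SPECT. Outcome 5 reads "Comparison of the diagnostic performance of FFR and RFR with SPECT ischemia". Section 9.2 plans an ROC analysis of RFR against SPECT ischaemia.

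Section 3.8 describes the scan as part of care: "In order to assist the Heart Team in deliberation over the ischemic importance of intermediate coronary lesions, SPECT imaging is clinically indicated", followed by "This will be carried out in the Department of Nuclear Medicine according to routine clinical practice". It also says "SPECT is also used to confirm the presence of ischemia". The revascularisation decision "based on intra-coronary measurements and non-invasive measures of ischemia (SPECT) is discussed by the Heart Team".

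The schedule of events (section 4) puts SPECT and catheterisation with FFR and IMR in the same baseline column, without an order. Sections 3.8, 8 and 9 contain no masking rule for the SPECT reader, no separate study read and no definition of a positive scan. Figures 1 and 2 were not available to this review.

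**The concern.** FFR and RFR are numeric outputs of a pressure wire. A SPECT call of ischaemia involves judgement, especially when a perfusion defect is equivocal. If the reader knows the FFR or RFR when settling such a scan, the reference standard partly contains the test it is meant to judge. Agreement then arises at the reading desk and cannot be told apart from physiological agreement. More patients would not remove it.

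Exposure is plausible. Under section 3.8, lesions found at angiography are wired during the same catheterisation. The SPECT ineligibility rules in section 3.6 (left main stenosis, triple vessel disease, tandem lesions) are largely angiographic. Wire values may therefore often exist before the scan is read.

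At stake are the expected validation of RFR in aortic stenosis, the comparison with the earlier iFR study, and the question of whether IMR improves FFR's prediction of ischaemia.

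**Working it through.** **The plan's own figure.** Section 9.1 takes 100 patients less 20%: 100 × 0.80 = 80. It states AUC 0.70 and two-sided alpha 0.05; the printed power of 0.90% is read as 90%. The null AUC and the prevalence of ischaemia are not given. Against an assumed null of 0.50, with the Hanley-McNeil variance (null variance under the null hypothesis), power at 80 is 0.818, 0.873 and 0.893 at prevalence 0.30, 0.40 and 0.50. Using the alternative variance only, it is 0.845, 0.903 and 0.928. So 80 is attainable at prevalence of about 0.40 to 0.50 but cannot be confirmed. The masking point does not depend on it, and masking does not change it.

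**Inputs for the illustration.**
- True AUC A = 0.70: the planned value in section 9.1, taken here as the truth.
- Share of patients test-positive, q: with FFR mean 0.82 and SD 0.08 (section 9.1), P(FFR ≤ 0.80) = Φ(−0.25) = 0.401.
- Prevalence p = 0.35: assumed.
- Share f of scans whose label is replaced by the wire result: assumed 5%, 10% or 20%. All of these follow the wire; the other labels are taken as correct.

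**Model.** Binormal, with separation d = √2 × Φ⁻¹(0.70) = 0.742. The cut c that makes 40.1% positive solves 0.35[1 − Φ(c − 0.742)] + 0.65[1 − Φ(c)] = 0.401, so c = 0.521. True sensitivity is 1 − Φ(0.521 − 0.742) = 0.587.

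The observed SPECT-positive share is P1 = (1 − f)p + fq. Among observed positives, w1 = (1 − f)p / P1 keep a true label. Among observed negatives, w0 = (1 − f)(1 − p) / (1 − P1) do. Then

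AUC = w1·w0·A + w1(1 − w0)·a + (1 − w1)w0·b + (1 − w1)(1 − w0),

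where a = 0.833 is the chance that a truly ischaemic patient ranks above a wire-negative one, and b = 0.867 the chance that a wire-positive patient ranks above a truly non-ischaemic one (both by integration). Apparent sensitivity = [(1 − f)p × 0.587 + fq] / P1.

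At f = 20%: P1 = 0.280 + 0.080 = 0.360; w1 = 0.777; w0 = 0.813. AUC = 0.442 + 0.121 + 0.157 + 0.042 = 0.762.

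| f | w1 | w0 | apparent AUC | apparent sensitivity |
|---|---|---|---|---|
| 0 | 1 | 1 | 0.700 | 0.587 |
| 5% | 0.943 | 0.954 | 0.716 | 0.611 |
| 10% | 0.887 | 0.907 | 0.731 | 0.634 |
| 20% | 0.777 | 0.813 | 0.762 | 0.679 |

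**Range.** With f = 20% and prevalence 20% to 50%, AUC runs from 0.77 to 0.76. A true AUC of 0.60 to 0.65 would read about 0.68 to 0.74, near or above the planned 0.70. If only half of the equivocal scans follow the wire, f halves: 10% equivocal then gives 0.716, not 0.731.

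**Objective 4.** A replaced label can never be FFR-negative and SPECT-positive, so the share of those patients shrinks by the factor 1 − f. It starts at 0.35 × (1 − 0.587) = 0.145 of all patients and falls to 0.8 × 0.145 = 0.116 at f = 20%. These are the patients in whom IMR is meant to correct a falsely high FFR.

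For the gain in AUC, assume that IMR is independent of FFR within ischaemia status and shifted by 0.5 SD. The true combined AUC is Φ(√(0.742² + 0.5²)/√2) = Φ(0.632) = 0.736, a gain of 0.036. With replaced labels, simulation gives gains of 0.030, 0.025 and 0.017 at f = 5%, 10% and 20%.

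**The case against.** The strongest reply is that the plan's silence does not show that the reader is exposed. The scan is done in a different department, and the Heart Team is described as receiving SPECT and the intra-coronary measurements as two inputs. That shows where the results meet, not that the SPECT reader holds the wire values. This stands: a reader might infer that the reads are contaminated, and the documents do not support that.

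The order is also open. Where SPECT is reported before catheterisation, this mechanism cannot operate. The schedule does not settle the matter, and the unavailable study-flow figures might.

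The illustration leans high. Prevalence and the equivocal share have no source in the documents, and every equivocal scan is made to follow the wire. At 80 patients and 35% prevalence (28 ischaemic, 52 not), the Hanley-McNeil standard error at AUC 0.70 is about 0.064. Shifts of 0.016 to 0.031 are then a quarter to a half of one standard error. That makes the bias hard to see in the data; it does not make it average out.

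What the reply does not remove is that a routine clinical read, as the stated method, does not secure the independence that the ROC analysis assumes. An unwritten local habit of masking would not show in the plan or support the published result.

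**Conclusion.** The point holds as a gap in protection, not as a demonstrated bias. The reference standard for secondary objectives 4 and 5 is a routine read made for the same Heart Team decision, and the available text neither masks it to FFR, RFR and IMR nor fixes its order relative to catheterisation.

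If equivocal scans were settled with the wire values in view, objective 5 would be biased upwards: a true AUC of 0.70 would read about 0.72 to 0.76 with full deference in 5% to 20% of scans at 35% prevalence, and less with partial influence.

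Two wider readings should be resisted. It is tempting to say that every SPECT-based result is inflated; for objective 4 the added value of IMR would more likely be understated, against the study's own hypothesis. Nor does the point reach the primary endpoint, the paired change in FFR, which does not use SPECT. It should be fixed, but it does not threaten the main result.

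**What to change.** Add to section 3.8:
- The reporting nuclear physician records a study SPECT result, ischaemia yes or no per coronary territory, before or without access to the FFR, RFR and IMR values.
- The result follows a prespecified definition of ischaemia that also says how equivocal scans are classified.
- The dates of the SPECT read and of the catheterisation are recorded.

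Add to section 9.2 that this recorded result is used in all analyses against SPECT.

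The clinical report and the Heart Team discussion can use all data as now. No extra scan, staff or patients are needed, and the target of 80 does not change. The cost is agreeing the definition and one recording step before the reader opens the wire data. Scans already reported with knowledge of the wire values should be flagged and examined in a sensitivity analysis, since the new step cannot repair them.
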